9.5.4.1 Reporting of Serious Adverse Events

All serious adverse events (SAEs), regardless of their relationship to study treatment, must be reported **as soon as possible but no later than 1 business day from the date the investigator becomes aware of the event. In addition, the investigator must report to the sponsor on a completed SAE form as soon as possible.**

Serious adverse events, regardless of causality assessment, must be collected through the study and for 70 days after the subject's last dose. All SAEs must be followed to resolution or, if resolution is unlikely, to stabilization. Any SAE judged by the investigator to be related to the study treatment or any protocol-required procedure should be reported to the sponsor regardless of the length of time that has passed since study completion.

Contact information of urgent safety issues is provided in Appendix 2.

It is very important that the SAE report form be filled out as completely as possible at the time of the initial report. This includes the investigator's assessment of causality.

Any follow-up information received on SAEs should be forwarded within 1 business day of its receipt. If the follow-up information changes the investigator's assessment of causality, this should also be noted on the follow-up SAE form.

Preliminary SAE reports should be followed as soon as possible by detailed descriptions including copies of hospital case reports, autopsy reports, and other documents requested by the sponsor.

9.5.4.2 Reporting of Pregnancy and Exposure to Study Drug Through Breastfeeding

Any pregnancy in which the estimated date of conception is either before the last visit or within 70 days of last study treatment, or any exposure to study drug through breastfeeding during study treatment or within 70 days of last study treatment, must be reported.

If an adverse outcome of a pregnancy is suspected to be related to study drug exposure, this should be reported regardless of the length of time that has passed since the exposure to study treatment.

A congenital anomaly, death during perinatal period, an induced abortion, or a spontaneous abortion are considered to be an SAE and should be reported in the same time frame and in the same format as all other SAEs (see Section 9.5.4.1 "Reporting of Serious Adverse Events").

Pregnancies or exposure to study drug through breastfeeding must be reported by fax or email as soon as possible but no later than 1 business day from the date the investigator becomes aware of the pregnancy. The contact information for the reporting of pregnancies and exposure to study drug through breastfeeding is provided in [Section 9.5.4.1](#). The pregnancy report form (Appendix 13) must be used for reporting. All pregnancies must be followed to outcome. The outcome of the pregnancy must be reported by the pregnancy outcome report form (Appendix 14) as soon as possible but no later than 1 business day from the date the investigator becomes aware of the outcome.

A subject who becomes pregnant must be withdrawn from the study.

9.5.4.3 Reporting of Events Associated with Special Situations

9.5.4.3.1 REPORTING OF ADVERSE EVENTS ASSOCIATED WITH STUDY DRUG OVERDOSE, MISUSE, ABUSE, OR MEDICATION ERROR

Adverse events associated with study drug overdose, misuse, abuse, and medication error refer to AEs associated with uses of the study drug outside of that specified by the protocol. Overdose, misuse, abuse, and medication error are defined as follows:

Overdose	Accidental or intentional use of the study drug in an amount higher than the protocol-defined dose.
Misuse	Intentional and inappropriate use of study drug not in accordance with the protocol
Abuse	Sporadic or persistent intentional excessive use of study drug accompanied by harmful physical or psychological effects
Medication error	Any unintentional event that causes or leads to inappropriate study drug use or subject harm while the study drug is in the control of site personnel or the subject.

All AEs associated with overdose, misuse, abuse, or medication error should be captured on the Adverse Event CRF and also reported using the procedures detailed in Reporting of Serious Adverse Events ([Section 9.5.4.1](#)) even if the AEs do not meet serious criteria. Abuse is always to be captured as an AE. If the AE associated with an overdose, misuse, abuse, or medication error does not meet serious criteria, it must still be reported using the SAE form and in an expedited manner but should be noted as nonserious on the SAE form and the Adverse Event CRF.

9.5.4.4 Expedited Reporting

The sponsor must inform investigators and the head of the medical institution and regulatory authorities of reportable events, in compliance with applicable regulatory requirements, on an expedited basis. For this reason, it is imperative that sites provide complete SAE information in the manner described above (see [Section 9.5.4.1](#) "Reporting of Serious Adverse Events").

9.5.4.5 Breaking the Blind

In the case of a medical emergency where the appropriate treatment of the subject requires knowledge of the study treatment given, the investigator may break the randomization code for an individual subject. In all such cases, the AE necessitating the emergency blind break will be handled as an SAE in accordance with the procedures indicated above (see [Section 9.5.4.1](#) "Reporting of Serious Adverse Events"). Any broken code will be clearly justified and documented. The sponsor must be notified immediately of the blind break.

Procedures for emergency blind break are as follows.

Procedures for emergency blind break

1. The investigator or the sponsor will request the emergency code center to break the subject's emergency unblinding code.
2. The emergency code center will obtain the necessary information (investigational site /department, name of person requesting blind break, drug number, study title, and the person to contact when returning the information) from the person requesting code breaking (the investigator or the sponsor).
3. If unblinding is judged appropriate, the emergency code center will unblinding the emergency code for the subject and promptly inform the result to the person to contact (the investigator or the sponsor).
4. When the unblinding request is made by an investigator, the emergency code center will promptly notify the sponsor of the necessary information obtained by the investigator and the result of unblinding.
5. When the unblinding request is made by the sponsor, the sponsor will notify the investigator of the reason, course, and result of the unblinding.

Contact information of the emergency code center is provided in Appendix 2.

9.5.4.6 Regulatory Reporting of Adverse Events

Adverse events will be reported to regulatory authorities in compliance with local law and established guidance. The format of these reports will be dictated by the local requirements.

9.5.5 Completion/Discontinuation of Subjects

A subject may elect to discontinue the study at any time for any reason. All subjects who discontinue the study are to complete the study's early discontinuation procedures indicated in the Schedule of Procedures/Assessments ([Section 9.5.2.1, Table 4](#)).

The investigator will promptly explain to the subject involved that the study will be discontinued for that subject and provide appropriate medical treatment and other necessary measures for the subject. A subject who has ceased to return for visits will be followed up by mail, phone, or other means to gather information such as the reason for failure to return, the

status of treatment compliance, the presence or absence of AEs, and clinical courses of signs and symptoms.

Subjects who discontinue early from the study will be discontinued for 1 of these primary reasons: AE(s), lost to follow-up, subject choice, inadequate therapeutic effect, progression of disease, withdrawal of consent, pregnancy, study terminated by sponsor, or other. In addition to the primary reason, the subject may indicate 1 or more secondary reason(s) for discontinuation. Study disposition information will be collected on the CRF.

9.5.6 Abuse or Diversion of Study Drug

Not applicable.

9.5.7 Confirmation of Medical Care by Another Physician

The investigator, subinvestigator, or clinical research coordinator will instruct subjects to inform site personnel when they are planning to receive medical care by another physician. At each visit, the investigator will ask the subject whether he/she has received medical care by another physician since the last visit or is planning to do so in the future. When the subject is going to receive medical care by another physician, the investigator or subinvestigator, with the consent of the subject, will inform the other physician that the subject is participating in the clinical study.

9.6 Data Quality Assurance

This study will be organized, performed, and reported in compliance with the protocol, SOPs, working practice documents, and applicable regulations and guidelines.

9.6.1 Data Collection

Data required by the protocol will be collected on the CRFs and entered into a validated data management system that is compliant with all regulatory requirements. As defined by GCP, the CRF is a printed, optical, or electronic document designed to record all of the protocol-required information to be reported to the sponsor on each study subject.

Data collection on the CRF must follow the instructions described in the CRF Completion Guidelines. The investigator has ultimate responsibility for the collection and reporting of all clinical data entered on the CRF. The investigator must sign the completed CRF to attest to its accuracy, authenticity, and completeness.

Completed, original CRFs are the sole property of Eisai and should not be made available in any form to third parties without written permission from Eisai, except for authorized representatives of Eisai or appropriate regulatory authorities.

9.6.2 Clinical Data Management

All software applications used in the collection of data will be properly validated following standard computer system validation that is compliant with all regulatory requirements. All data, both CRF and external data (eg, laboratory data), will be entered into a clinical system.

9.7 Statistical Methods

Statistical analyses will be performed by using SAS or other validated statistical software as needed after unblinding. In this study, the statistical analysis in the Treatment Phase will be performed after the database in the Treatment Phase is locked and the data is unblinded, and then final analysis will be performed by using all data after the database throughout the study period is locked. The details will be described separately in the Statistical Analysis Plan (SAP). SAP for the Treatment Phase and the entire study (the Treatment and Extension Phases) will be finalized before each database lock.

9.7.1 Statistical and Analytical Plans

The statistical analyses of study data are described in this section. Analyses in the Treatment Phase are mainly described in the following sections to [Section 9.7.1.8](#), while analyses in the Extension Phase are described in [Section 9.7.1.9](#).

9.7.1.1 Study Endpoints

9.7.1.1.1 PRIMARY ENDPOINT

- ACR20 response rate at Week 12

ACR20 response rate: A subject is defined as ACR20 responder if all of the following 3 criteria are met, and ACR 20 response rate refers to the percentage of subjects with ACR20 response:

1. Greater than or equal to 20% reduction from baseline in the tender joint counts (out of 68 joints)
2. Greater than or equal to 20% reduction from baseline in the swollen joint counts (out of 66 joints)
3. Greater than or equal to 20% reduction from baseline in at least 3 of the following 5 assessments:
 - Physician's disease activity assessment
 - Patient's disease activity assessment
 - Patient's pain assessment
 - HAQ
 - CRP

9.7.1.1.2 SECONDARY ENDPOINTS

- ACR20, ACR50, and ACR70 response rates at each evaluation time point (excluding ACR20 response rate at Week 12)
- Values and change from baseline in ACR components (number of tender joints, number of swollen joints, VAS [Patient's pain assessments/disease activity global assessments and physician's disease activity global assessment], patient's physical function assessment [HAQ], and CRP/ESR), DAS28-ESR, DAS28-CRP, SDAI, and CDAI at each evaluation time point
- EULAR response criteria and disease activity classification based on DAS28-ESR or DAS28-CRP at each evaluation time point
- Remission rate calculated based on each remission criterion (DAS28-ESR, DAS28-CRP, SDAI, CDAI, and Boolean) at each evaluation time point
- Values and change from baseline in mTSS at each evaluation time point

The ACR50 response rate is defined similarly to the ACR20 response rate, except for a 50% reduction as threshold.

The ACR70 response rate is defined similarly to the ACR20 response rate, except for a 70% reduction as threshold.

DAS28-CRP: This will be calculated on the following formula, and disease activity is categorized as High at >4.1 , Moderate at >2.7 and ≤ 4.1 , Low at ≤ 2.7 , and Remission at <2.3 .

$$0.56 \times \sqrt{[\text{Number of tender joints (28 joints)}]} + 0.28 \times \sqrt{[\text{Number of swollen joints (28 joints)}]} + 0.36 \times \ln(\text{CRP} \times 10 + 1) + 0.014 \times \text{Patient's disease activity assessments} + 0.96$$

DAS28-ESR: This will be calculated on the following formula, and disease activity is categorized as High at >5.1 , Moderate at >3.2 and ≤ 5.1 , Low at ≤ 3.2 , and Remission at <2.6 .

$$0.56 \times \sqrt{[\text{Number of tender joints (28 joints)}]} + 0.28 \times \sqrt{[\text{Number of swollen joints (28 joints)}]} + 0.70 \times \ln(\text{ESR}) + 0.014 \times \text{Patient's disease activity assessments}$$

EULAR Response Criteria:

Present DAS28	DAS28 reduction from baseline		
	<-1.2	≥-1.2 and <-0.6	≥-0.6 (missing included)
Low	Good response	Moderate response	No response
Moderate	Moderate response	Moderate response	No response
High	Moderate response	No response	No response

The CDAI will be calculated on the following formula, and disease activity is categorized as High at >22 , Moderate at >10 and ≤ 22 , Low at ≤ 10 , and Remission at ≤ 2.8 .

Number of swollen joints (28 joints) + Number of tender joints (28 joints)
+ Patient's disease activity assessments/10
+ Physician's disease activity assessment/10

SDAI: This will be calculated on the following formula, and disease activity is categorized as High at >26 , Moderate at >11 and ≤ 26 , Low at ≤ 11 , and Remission at ≤ 3.3 .

Number of swollen joints (28 joints) + Number of tender joints (28 joints)
+ Patient's disease activity assessments/10
+ Physician's disease activity assessment/10+CRP

Boolean remission: A subject is judged to have Boolean remission if all of the following conditions are satisfied:

1. Tender joint counts (out of 68 joints) ≤ 1
2. Swollen joint counts (out of 66 joints) ≤ 1
3. CRP ≤ 1
4. Patient's disease activity assessment ≤ 10

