3 INTRODUCTION

The purpose of this statistical analysis plan (SAP) is to describe the procedures and the statistical methods that will be used to analyze and report results for Eisai Protocol E6011-J081-201. Since the Version 6 of the protocol defined that it was unnecessary to conduct assessments other than safety assessment, all the efficacy analysis will be conducted until Week 84, that is the latest Visit of ongoing subjects at the time of amendment of the protocol.

Statistical methods of Extension Phase are provided in this document.

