5.1.2 Secondary Endpoints

- ACR20, ACR50, and ACR70 response rate at each visit (excluding ACR20 at Week 12)
- Values and change from baseline in ACR components (TJC, SJC, VAS [patient's assessment of pain, patient's global assessment of disease activity and physician's global assessment of disease activity], functional assessment by subjects [HAQ-DI], and CRP·ESR), DAS28-ESR, DAS28-CRP, SDAI, and CDAI at each visit
- EULAR response criteria at each visit; subjects will be classified based on DAS28-ESR or DAS28-CRP
- DAS28-ESR, DAS28-CRP, SDAI, CDAI, and Boolean remission rates at each visit
- Values and change from baseline in modified total sharp score (mTSS) at each visit

The ACR50 response is defined similar to the ACR20 with a 50% reduction.

The ACR70 response is defined similar to the ACR20 with a 70% reduction.

The DAS28-CRP calculates on the following formula, and disease activity is categorized as High at > 4.1 , Moderate at > 2.7 and ≤ 4.1 , Low at ≤ 2.7 , and Remission at ≤ 2.3 .

$$0.56 \times \text{sqrt}\{\text{TJC in 28 joints (TJC28)}\} + 0.28 \times \text{sqrt}\{\text{SJC in 28 joints (SJC28)}\} + 0.36 \times \ln\{\text{CRP (mg/dL)} \times 10 + 1\} + 0.014 \times \text{Patient's Global Assessment of Disease Activity (VAS) (mm)} + 0.96$$

The DAS28-ESR will be calculated on the following formula, and disease activity is categorized as High at > 5.1 , Moderate at > 3.2 and ≤ 5.1 , Low at ≤ 3.2 , and Remission at < 2.6 .

$$0.56 \times \text{sqrt}\{\text{TJC28}\} + 0.28 \times \text{sqrt}\{\text{SJC28}\} + 0.70 \times \ln\{\text{ESR (mm/h)}\} + 0.014 \times \text{Patient's Global Assessment of Disease Activity (VAS) (mm)}$$

EULAR Response Criteria:

Present DAS28	DAS28 change from baseline		
	<-1.2	≥ -1.2 and <-0.6	≥ -0.6 (missing included)
Low	Good response	Moderate response	No response
Moderate	Moderate response	Moderate response	No response
High	Moderate response	No response	No response

The CDAI will be calculated on the following formula, and disease activity is categorized as High at > 22 , Moderate at > 10 and ≤ 22 , Low at ≤ 10 , and Remission at ≤ 2.8 .

$$\begin{aligned} & \text{SJC28} + \text{TJC28} \\ & + \text{Patient's Global Assessment of Disease Activity (VAS) (mm)/10} \\ & + \text{Physician's Global Assessment of Disease Activity (VAS) (mm)/10} \end{aligned}$$

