8.1.2 Definition of change from baseline and percent change from baseline

Change from baseline is defined as postbaseline value minus baseline value. Percent change from baseline is defined as follows:

$$\% \text{ Change from baseline} = (\text{Change from baseline}/\text{Baseline}) * 100$$

For any Baseline value of 0, the subject's corresponding percent change from baseline will not be included in the summary statistics table.

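### The protocol's EULAR response table is headed as a DAS28 reduction but carries the negative limits of a signed change; read literally, it classes every improver as a non-responder

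*Protocol*

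**What the plan says.** Protocol 9.7.1.1.2 gives a three-by-three EULAR table. The rows are the present DAS28 category. The columns are headed "DAS28 reduction from baseline", with limits <-1.2, then ≥-1.2 and <-0.6, then "≥-0.6 (missing included". The last column is *No response* in every row.

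The row bands for DAS28-ESR are "categorized as High at >5.1 , Moderate at >3.2 and ≤ 5.1 , Low at ≤ 3.2", and for DAS28-CRP "categorized as High at >4.1 , Moderate at >2.7 and ≤ 4.1 , Low at ≤ 2.7".

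The protocol's other use of the word is in the ACR20 definition in 9.7.1.1.1: "Greater than or equal to 20% reduction from baseline in the tender joint counts (out of 68 joints". There, a reduction is a positive amount of improvement. The protocol states no convention that would make a reduction negative.

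SAP 5.1.2 prints the same limits and the same nine cells under the heading "DAS28 change from baseline". SAP 8.1.2 fixes the sign: "Change from baseline is defined as postbaseline value minus baseline value". On scope, SAP section 3 says: "Statistical methods of Extension Phase are provided in this document". Protocol 9.7 provides for a SAP for the Treatment Phase as well; it is not among the documents reviewed.

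**The concern.** The heading and the limits in the protocol table belong to opposite sign conventions. A fall of 2 points is a reduction of +2, which lies above -0.6 and so falls in the *No response* column. A reduction below -1.2 is a worsening of more than 1.2 points, and it falls in the column that holds *Good response* and *Moderate response*. As printed, the rule runs backwards.

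EULAR response is a named secondary endpoint at each evaluation time point, on both DAS28-ESR and DAS28-CRP. In the documents available, the protocol table is the only definition specific to the placebo-controlled phase. Protocol 9.7.1.9 asks for extension analyses similar to those of the Treatment Phase, so the two phases should share one definition. As worded, the protocol and the SAP give it opposite signs. Neither the amendment overviews nor the list of changes in SAP section 7 mentions the difference.

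**Working it through.** The plan states no figure for this item, so there is nothing to reproduce. The check applies the table under both headings.

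**Inputs.** Column limits and cells from protocol 9.7.1.1.2 (identical in SAP 5.1.2), the activity bands quoted above, and the sign of change from SAP 8.1.2.

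**Formulas.** Literal reading: x = baseline − present. Intended reading: x = present − baseline.

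**Individual records, DAS28-ESR.**

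| Baseline → present | Present category | Reduction | As printed | Change | As intended |
|---|---|---|---|---|---|
| 6.1 → 3.0 | Low | +3.1 | No | -3.1 | Good |
| 5.8 → 4.2 | Moderate | +1.6 | No | -1.6 | Moderate |
| 4.5 → 5.8 | High | -1.3 | Moderate | +1.3 | No |
| 4.0 → 4.8 | Moderate | -0.8 | Moderate | +0.8 | No |
| 1.8 → 3.1 | Low | -1.3 | Good | +1.3 | No |
| 4.5 → 5.4 | High | -0.9 | No | +0.9 | No |
| 6.0 → 5.3 | High | +0.7 | No | -0.7 | No |

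The first five records are misclassified by the printed rule. The last two are classed the same either way.

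**General result.** Any improver has a positive reduction, hence x ≥ -0.6, hence *No response* in every row. A worsening of more than 1.2 gives x < -1.2, which is *Good* in the Low row and *Moderate* in the other two. A worsening above 0.6 and up to 1.2 falls in the middle column, which is *Moderate* in the Low and Moderate rows and *No response* in the High row.

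**Exhaustive check.** Take all pairs of baseline and present values from 1.0 to 9.0 in steps of 0.1: 81 × 81 = 6561 pairs, of which 3240 improve, 3240 worsen and 81 are unchanged. The unchanged pairs are *No response* under both readings.

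| Index and reading | Improving: Good / Moderate / No | Worsening: Good / Moderate / No |
|---|---|---|
| ESR, as printed | 0 / 0 / 3240 | 55 / 2486 / 699 |
| ESR, as intended | 1311 / 1287 / 642 | 0 / 0 / 3240 |
| CRP, as printed | 0 / 0 / 3240 | 15 / 2466 / 759 |
| CRP, as intended | 1071 / 1467 / 702 | 0 / 0 / 3240 |

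The worsening pairs that stay *No response* under the printed rule are accounted for as follows. Worsening of 0.1 to 0.6 gives 80 + 79 + 78 + 77 + 76 + 75 = 465 pairs. Worsening of 0.7 to 1.2 that ends in High gives 6 × 39 = 234 pairs for ESR and 6 × 49 = 294 for CRP. The totals are 465 + 234 = 699 and 465 + 294 = 759.

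These counts show direction only; they are not expected frequencies in the trial. In particular, a *Good response* in a worsening subject needs a baseline DAS28-ESR below 2.0 (present ≤3.2 after a rise of more than 1.2), which is unlikely given the joint-count entry criteria. A *Moderate response* in a worsening subject needs no unusual baseline.

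**The case against.** The strongest reply is that the slip reveals itself. A table that gives its best grade to Low activity with a value below -1.2, and no response to values of -0.6 and above, makes sense only for present minus baseline. The endpoint list in the same protocol section also speaks of change from baseline for DAS28. The SAP has the right heading and defines the sign, and its endpoint section restates the whole study's endpoints, including ACR20 at Week 12. A careful programmer would probably code it correctly. All of this stands, and it keeps the point small. It does not make the printed protocol rule correct.

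A reader might infer that the EULAR results of the placebo-controlled phase are reversed. The documents do not support that. It would require the heading to have been programmed literally, and nothing shows that this was planned or done. The Treatment Phase SAP may already carry the right heading.

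A reader might also infer that the printed rule is right only for subjects with a trivial change. That is too strong. Four kinds of non-responder are classed the same under both readings: those with an improvement too small to count, those with no change, those who worsen by up to 0.6, and those who worsen by more than 0.6 and up to 1.2 and end in High, such as DAS28-ESR 4.5 to 5.4.

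**Conclusion.** The point holds as an error in the wording of an operative endpoint definition. Taken as printed, with reduction meaning a positive fall, the protocol table misclassifies all true good and moderate responders. It also counts as responders those who worsen by more than 1.2 points, or by more than 0.6 points without ending in High. Whether any result is affected depends on the Treatment Phase SAP and programs, which were not seen.

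The importance is low. The classification is secondary and is reported in shift tables (protocol 9.7.1.6.2; SAP 5.4.2), with no multiplicity adjustment for secondary analyses. The primary analysis, alpha and sample size are unaffected.

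**What to change.** In protocol 9.7.1.1.2, replace the column heading with "DAS28 change from baseline" (postbaseline minus baseline), leaving limits and cells as they are. This matches SAP 5.1.2 and 8.1.2. Then confirm that the Treatment Phase SAP and the Treatment Phase EULAR tables use that sign; checking the classification of one clear improver would show it.

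A note in section 7 of the supplied SAP would not be enough: that SAP already has the right heading, and its methods are for the Extension Phase, so it would not govern the Treatment Phase.

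The cost is one heading and one check, with no new data. Reanalysis would be needed only if the check showed that the literal sign had been programmed.
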